7. MMSE-2:SV
8. Six Minute Walk Test (6MWT) (Not required for CAP subjects enrolled under Ver. K or later)

9. Troponin or CK/CK-MB, INR (if subject is on Coumadin or Warfarin)

## 6.9 Subject Enrollment and Randomization

All subjects who meet the study eligibility requirements will be assigned into an applicable registry (Roll-in or Valve-in-Valve), the FlexNav study, the CAP or one of the pivotal IDE randomized cohorts for operability, followed by delivery method determination based on vascular access (Figure 10).

Subjects will be considered enrolled into the study after completion of all of the following steps:

1. Signed informed consent is obtained.
2. Based on the screening assessments, it is determined that the subject meets all of the inclusion and none of the exclusion criteria.
3. Subject is approved by the subject selection committee.
4. The trial cohort has been determined, and understood by the subject.
5. The subject is randomized (pivotal IDE only) or assigned to the appropriate registry or CAP.

In the FlexNav study and the CAP (under protocol version L), the subject will be considered enrolled once steps 1-4 above are complete and when the FlexNav™ Delivery System enters the subjects' body.

[figure not shown]
For the pivotal randomized IDE cohort, the subject will be randomized based on the cohort assignment as follows:

- The high risk cohort will be randomized against an FDA-approved and commercially-available transcatheter valve on a 1:1 basis.
- The extreme risk cohort will be randomized against an FDA-approved and commercially-available transcatheter valve on a 1:1 basis.

It is strongly recommended the implant procedure take place no later than 14 calendar days from subject enrollment/randomization

Once a subject is randomized in the pivotal IDE, crossover from one arm to the other is not allowed. However, following randomization or enrollment in the FlexNav Study, registry or the CAP, those subjects who are scheduled to receive a transcatheter valve via transfemoral access and found not to be suitable for this delivery modality (per the heart team medical decision) can receive a transcatheter valve using an alternate access modality and vice versa. However, this will be considered a protocol deviation unless multiple access routes were pre-approved by the Subject Selection Committee. The rationale for this decision must be documented.

In the pivotal IDE trial, when subjects are randomized to receive a CAV, the subject selection and procedure must follow the FDA-approved instructions for use (IFU).

TF=Transfemoral, CAV= FDA approved and commercially available transcatheter valve, AA=Alternative Access, V-in-V=Valve-in-Valve

Figure 10. PORTICO Clinical Study Flow Chart

## **7 Study Conduct (Pivotal IDE and CAP)**

### **7.1 Subject Informed Consent**

Prior to enrolling in the clinical investigation, subjects shall be fully informed of the details of clinical investigation participation as required by applicable regulations and the center's IRB. Informed consent must be obtained from each subject prior to any clinical investigation participation (including the study-specific screening phase), using the Informed Consent Form (ICF). The ICF must be signed and dated by the subject and by the person obtaining the consent.

The subject shall be provided ample time to meet with the Site Principal Investigator or site personnel conducting the consent, and must be given the opportunity to ask questions of and receive satisfactory answers. The subject will then be allowed additional time, if requested, to take a copy of the informed consent form home with him or her to allow for additional time to thoroughly review this documentation.

All information pertinent to the clinical investigation shall be provided in writing and in native, non-technical language that is understandable to the subject.

The process of informed consent shall avoid any coercion of or undue influence of patients to participate, not waive or appear to waive patient's legal rights, use language that is non-technical and understandable to the patient, provide ample time for the patient to consider participation, and include dated signatures of the patient and of the clinical investigator or person obtaining the consent.

Prior to the subject signing the ICF, the Investigator or authorized delegate will fully explain to the subject the nature of the research, clinical investigation procedures, anticipated benefits, and potential risks of participation in the clinical investigation. The Investigator or delegate will allow adequate time for the subject to read and review the informed consent form and to ask questions.

The Investigator or authorized delegate must document in the subject's medical records that the subject was consented and the date on which the consent was obtained. The original signed informed consent form will be retained in the subject's clinical investigation records. A copy of the signed informed consent form and will be provided to the subject and a copy placed in the subject's medical record.

If new information becomes available during the clinical investigation that can significantly affect a subject's future health and medical care, or willingness to continue in the study, that information will be provided to the subject(s) in written form.

### **7.2 Subject Selection Committee**

The Subject Selection Committee will be responsible for ensuring all subjects' clinical eligibility and technical suitability for implant according to the protocol. The composition and detailed process is further defined in the Subject Selection Committee Charter.

Subject Selection Committee review and approval is required prior to enrollment of any subject into any randomized cohort, FlexNav study, registry or the CAP.

### **7.3 Index Procedure**

The heart team's interventional cardiologist(s) and cardiac surgeon(s) must jointly participate in the intra-operative technical aspects of TAVR.

The index procedure should occur within 14 calendar days following subject randomization, registry or CAP assignment. The procedure must be performed according to the instructions for use (IFU) for the assigned device. Antiplatelet/Anticoagulation and other medications should be administered per the standard of care.

Cardiac enzymes must be obtained prior to the index procedure and within approximately 72 hours after the procedure.

Cardiac rhythm should be monitored and recorded at the following time points:

1. Upon crossing native valve with the guidewire
2. Upon positioning of the guidewire
3. Prior to valvuloplasty (if performed)
4. Immediately post valvuloplasty (if performed)
5. Before valve crosses the AV valve
6. After valve crosses the annulus
7. After valve is deployed in final position

The following data should be collected pre and post implant:

1. Aortic systolic/diastolic pressure, Mean aortic pressure, Mean AV gradient, Peak AV gradient
2. Simultaneous Aortic and LV pressure measurements for valve area calculation
3. A supra-aortic angiogram for valve performance and coronary patency
4. Device deployment information
5. If performed, right atrial (RA) pressure, pulmonary artery (PA) systolic/diastolic pressure, Mean PA pressure, pulmonary wedge pressure (PCWP)

The activated clotting time (ACT) should be monitored and recorded on source documentation during the procedure and adjusted to attempt to keep the subject's ACT > 250 seconds.

If an enrolled subject is not implanted with a TAVR valve, the following will apply:

- Randomized subjects will be followed per protocol through the one-year visit, as part of the primary analysis intent to treat (ITT) population, and then terminated from the study.
- Registry-assigned (Roll-in or Valve-in-Valve), FlexNav study and CAP subjects will be assessed for any adverse events through 30 days post procedure, and then terminated from the study.

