#### Descriptive Endpoints:

1. Acute device success defined as:
  - Absence of procedural mortality AND
  - Correct positioning of a single prosthetic heart valve into the proper anatomical location AND
  - Intended performance of the prosthetic heart valve (mean aortic valve gradient <20 mmHg or peak velocity <3 m/s, no moderate or severe prosthetic valve regurgitation) AND
  - Successful access was obtained as intended by group assignment
2. Kansas City Cardiomyopathy Questionnaire (KCCQ) at one year for Centers for Medicare and Medicaid Services (CMS) National Coverage Decision primary quality of life endpoint
3. Major vascular complications at 30 days from the index procedure
4. NYHA functional classification at 30 days, 6 months, and one year
5. Six-minute walk test at 30 days, 6 months, and one year
6. Paravalvular Leak (PVL) at 30 days, 6 months, and one year

[REDACTED]

7. Aortic insufficiency greater than trace at 30 days, 6 months, one year, and two years
8. Reintervention to treat aortic insufficiency at 1 year and 2 years
9. Permanent pacemaker insertion at 30 days from the index procedure
10. Major bleeding at 30 days from the index procedure
11. Acute kidney injury at 30 days from the index procedure
12. Individual components of the primary effectiveness endpoint
  - All-cause mortality at 30 days, 6 months, one year and two years
  - Disabling stroke at 30 days, 6 months, one year and two years
13. Non-disabling Stroke and Transient Ischemic Attack (TIA) at 30 days, 6 months, one year, and two years
14. Atrial fibrillation at one year and two years
15. Quality of Life (QOL) from baseline to 30 days, 6 months and one year

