### **7.8 One-Year Visit (-30 days, + 45 days)**

The following data must be collected at one-year (-30 days, + 45 days) post index procedure:

1. Physical exam
2. CCS status of angina
3. Modified Rankin Scale (mRS)
4. NIH Stroke Scale (NIHSS)
5. Barthel Index
6. Echocardiography
7. 12 lead ECG (for subjects receiving a new permanent pacemaker, ECG should be completed showing the underlying rhythm as well as the current pacing programming)
8. Lab Measurements (per Table 9, Table of Assessments)
9. NYHA Functional Classification
10. Frailty Index assessment
11. Quality of Life Measures (QoL) (For CAP subjects enrolled under Ver. K or later, only the KCCQ and EQ-5D are required.)

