## 9.6 Subject Death

Subject death is a potential outcome of a Serious Adverse Event that will be reported within three (3) calendar days from the time of the site personnel knowledge of the event, if the event occurs from the time of signed informed consent until the subject exits the study.

Subject death will be subdivided specifically denoting cardiovascular and non-cardiovascular mortality:

1. Cardiovascular mortality includes any one of the following criteria:
  - a. Any death due to proximate cardiac cause (such as MI, tamponade, worsening heart failure)
  - b. Sudden or unwitnessed death
  - c. Death of unknown cause
  - d. All procedure-related deaths including those related to a complication of the procedure or treatment for a complication of the procedure
  - e. Death caused by non-coronary vascular conditions such as cerebrovascular disease, pulmonary embolism, ruptured aortic aneurysm, dissecting aneurysm, or other vascular disease.
2. Non-cardiovascular mortality includes any death in which the primary cause of death is clearly related to another condition (e.g. trauma, cancer, suicide)

An Adverse Event CRF, Death CRF and relevant source documentation including the death certificate should be submitted to SJM.

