**11.7.4 Analysis of Descriptive Endpoints**

The descriptive endpoints listed in section 1.3 will be summarized using descriptive statistics including mean, standard deviation, median and range for continuous data and count and percentage for categorical data.

[Redacted text block]

[Redacted text block]

[Redacted text block]

[Redacted text block]

[Redacted text block]

[REDACTED]

[REDACTED]

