## 12 Study Termination/Withdrawal (Pivotal IDE and CAP)

Active subject participation in the pivotal IDE is expected to last for five (5) years after index procedure unless the subject was randomized or assigned to a registry or FlexNav study but not implanted with a TAVR valve. Enrolled CAP subjects successfully implanted with a Portico valve will be followed for a minimum of one year and up to 5 years or upon study completion (whichever is reached first).

If an enrolled subject was not implanted with a TAVR valve, the following will apply:

- Randomized subjects will be followed per protocol through to the one-year visit, as part of the primary analysis intent to treat (ITT) population, and then terminated from the study.
- Registry-assigned (Roll-in or VIV Registry), FlexNav study or CAP subjects will be assessed for any adverse events through 30 days post procedure, and then terminated from the study.

The study will be closed at the investigational site following the distribution of the final clinical study report for all study locations. A copy of the final report will be provided to the IRB and Competent Authorities, if applicable, and acknowledgement requested.

Early termination of the study by either SJM or the Investigator, if applicable, will be communicated to the IRB.

Upon completion of subject participation in this study, the subject will be followed-up in accordance with institutional standards.

Possible reasons for early termination of the study and/or investigation site's participation in the study may include, but are not limited to:

- Request from the Clinical Investigation Site Principal Investigator
  - Delivery system or device fails to perform as intended
  - Occurrence of UADE which cannot be prevented in future cases
  - SJM management decision to discontinue the study
- [REDACTED]
- [REDACTED]

- Request from Regulatory bodies
- Site's noncompliance with the requirements of the CIP and/or applicable laws and regulations
- Falsification of data or any other breach of ethics or scientific principles

Subjects must be informed about their right to withdraw from the study at any time and for any reason without sanction, penalty, or loss of benefits to which the subject is otherwise entitled and withdrawal from the study will not jeopardize their future medical care or their relationship with the Principal Investigator. Subjects will be asked what the reason for termination is but have the right not to answer.

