 - o Correct positioning of a single prosthetic heart valve into the proper anatomical location AND
 - o Intended performance of the prosthetic heart valve (mean aortic valve gradient <20 mmHg or peak velocity <3 m/s, no moderate or severe prosthetic valve regurgitation) AND
 - o Successful access was obtained as intended by group assignment
2. Kansas City Cardiomyopathy Questionnaire (KCCQ) at one year for Centers for Medicare and Medicaid Services (CMS) National Coverage Decision primary quality of life endpoint
3. Major vascular complications at 30 days from the index procedure
4. NYHA functional classification at 30 days, 6 months, and one year
5. Six-minute walk test at 30 days, 6 months, and one year
6. Paravalvular Leak (PVL) at 30 days, 6 months, and one year
7. Aortic insufficiency greater than trace at 30 days, 6 months, one year, and two years
8. Reintervention to treat aortic insufficiency at 1 year and 2 years
9. Permanent pacemaker insertion at 30 days from the index procedure
10. Major bleeding at 30 days from the index procedure
11. Acute kidney injury at 30 days from the index procedure
12. Individual components of the primary effectiveness endpoint
 - o All-cause mortality at 30 days, 6 months, one year and two years
 - o Disabling stroke at 30 days, 6 months, one year and two years
13. Non-disabling Stroke and Transient Ischemic Attack (TIA) at 30 days, 6 months, one year, and two years
14. Atrial fibrillation at one year and two years
15. Quality of Life (QOL) from baseline to 30 days, 6 months and one year

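### Randomized subjects not implanted with a TAVR valve leave follow-up at a one-year visit that may fall on day 335, so some late one-year events and all their two-year outcomes need not be collected

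*Protocol*

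**What the plan says.** - **Follow-up without a TAVR valve.** Protocol 7.3 says these randomized subjects are "followed per protocol through the one-year visit, as part of the primary analysis intent to treat (ITT) population, and then terminated from the study". Section 12 repeats the rule. It expects pivotal subjects to take part for five years after the procedure, "unless the subject was randomized or assigned to a registry or FlexNav study but not implanted with a TAVR valve".
- **Visit window.** Section 7.8: "The following data must be collected at one-year (-30 days, + 45 days) post index procedure".
- **Time to procedure.** Section 6.9 strongly recommends that the implant procedure "take place no later than 14 calendar days from subject enrollment/randomization".
- **Death reporting.** Section 9.6 applies its three-day reporting rule to a death "if the event occurs from the time of signed informed consent until the subject exits the study".
- **Endpoints.** The primary effectiveness endpoint is death or disabling stroke at one year. Item 12 of the descriptive endpoints extends both components to two years: "All-cause mortality at 30 days, 6 months, one year and two years" (Protocol 1.3.1) and "Disabling stroke at 30 days, 6 months, one year and two years" (SAP 1.4.1).
- **Summary method.** Protocol 11.7.4 covers the descriptive endpoints of section 1.3 by name and prescribes "count and percentage for categorical data".
- **Blinding.** Under SAP 1.6, neither subjects nor implanters were blinded.

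**The concern.** The rule turns on the TAVR valve. It therefore covers subjects who never reach a procedure, failed attempts, and anyone converted to surgical valve replacement, a possibility listed in Protocol 4.1 and 9.3. All of them count in the primary ITT population.

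Two losses follow. First, a subject seen on day 335 can exit in full compliance and die on day 350 without any duty to report the death, although the endpoint runs to one year. Implanted subjects do not have this gap, because they stay in the study after an early visit. Second, two-year status is missing by design for exactly these subjects. Whether a subject is implanted is decided after randomization, and the share may differ between the arms. These subjects may also have a different prognosis. A two-year comparison by randomized arm could then be distorted.

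**Working it through.** **Day arithmetic (Protocol 7.8, 6.9).** The earliest one-year visit is 365 − 30 = day 335 and the latest is 365 + 45 = day 410. Up to 30 days before day 365 can go unobserved. If one year is counted from randomization and an attempted procedure took place 14 days later, the earliest visit is 335 + 14 = day 349, and 365 − 349 = 16 days can be lost.

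**One-year endpoint.** The only input from the documents is N = 750. Assumptions: 2–5% not implanted (750 × 0.02 = 15 to 750 × 0.05 = 37.5), annual mortality *m* of 25–50% in these subjects, constant hazard. With *n* subjects exiting on day *d*, deaths missed = *n* × [(1 − *m*)^(*d*/365) − (1 − *m*)].

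- All exit on day 335: 15 × (0.7679 − 0.75) = 0.27, up to 37.5 × (0.5293 − 0.50) = 1.10. This is the upper bound.
- All exit on day 349: 15 × (0.7595 − 0.75) = 0.14, up to 37.5 × (0.5154 − 0.50) = 0.58.
- 40% exit a mean of 15 days early: 0.4 × 15 × (0.7589 − 0.75) = 0.05, up to 0.4 × 37.5 × (0.5144 − 0.50) = 0.22.

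These figures count deaths only. As a cross-check on the composite, assume a one-year event rate of 10–30%. The chance of an event in days 335–365 is then 0.8–2.1%. With 1–5% not implanted (7.5 to 37.5 subjects), all seen on day 335, 0.06 to 0.8 events are missed.

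**Two-year mortality by randomized arm.** Let *p* be the share not implanted, *m* their annual mortality, and *a* and *b* the mortality of implanted subjects in years one and two.

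- True = 1 − [*p*(1 − *m*)² + (1 − *p*)(1 − *a*)(1 − *b*)]
- Observed deaths over all randomized: D = *pm* + (1 − *p*)[1 − (1 − *a*)(1 − *b*)], so true − D = *pm*(1 − *m*)
- Observed deaths over subjects with known two-year status: D / [D + (1 − *p*)(1 − *a*)(1 − *b*)]

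Example: *p* = 4% (test) and 2% (control), *m* = 0.35, *a* = 0.15, *b* = 0.10 in both arms. True mortality is 24.87% and 24.19%. Over all randomized it reads 23.96% and 23.73%. Over known status it reads 24.60% and 24.04%.

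Differences, test minus control, in percentage points (every rate is assumed):

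| Scenario | True | All randomized | Known status |
|---|---|---|---|
| *p* 4% vs 2%, *m* 0.35, *a* 0.15 and *b* 0.10 in both arms | +0.69 | +0.23 | +0.56 |
| Same, but test *a* 0.14, *b* 0.09 | −1.00 | −1.46 | −1.18 |
| *p* 4% vs 2%, *m* 0.20, *a* 0.15 and *b* 0.10 in both arms | +0.25 | −0.07 | +0.32 |
| *p* 3% in both arms, *m* 0.35, *a* 0.15 and *b* 0.10 | 0 | 0 | 0 |

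The third row uses a lower mortality than the 25–50% above, to show how far the result depends on it. In the fourth row each arm reads 23.84% or 24.32% instead of 24.53%, but the difference is unaffected.

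**The case against.** The strongest reply is that the rule is explicit, stated consistently in two places, and keeps these subjects in ITT through the visit that serves the primary endpoint. What is lost is about one event or fewer of 750 subjects, plus descriptive data without a hypothesis test. The rates are assumed, and the two-year effect grows, shrinks or vanishes with them. All of this stands, and it limits the point to a minor one.

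Redaction is a further reply. The ITT definition and much of the analysis text are blacked out and may set a time origin or a censoring rule. So one cannot say that the plan lacks a day 0 for subjects who never had a procedure. But the termination rule, the visit window and the death-reporting rule are all legible, and analysis text cannot supply data that the protocol stops collecting. Section 9.4.1 has unresolved adverse events followed to resolution, which helps for an event already reported but not for a new one after exit.

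A reader might infer three stronger things:

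- **The primary lock will come before complete data.** The visible sentence in SAP 2.3.1 names neither day 365 nor a pending 90-day mRS. It sets only an earliest lock date, and redacted text follows it. A gap before day 365 arises only if the lock falls within days of a very early last visit.
- **The two-year ITT comparison is biased.** The visible text does not name the population for the two-year summaries, and SAP 2.1 also provides As Treated and Per Protocol results.
- **The choice between Kaplan-Meier and percentages is open.** Protocol 11.7.4 settles on counts and percentages for these endpoints. Only the denominator is unstated.

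**Conclusion.** The point holds as a minor gap in ascertainment. Following the legible rules as written, randomized subjects without a TAVR valve can leave up to 30 days before the primary endpoint is complete, and their two-year status is not collected.

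The effect on the one-year endpoint is 0.05 to 1.1 missed deaths under the assumed rates, so nothing here suggests that the primary non-inferiority result is in danger. If the two-year endpoints are summarized by randomized arm, the mortality difference moves by about 0.1 to 0.5 points in the unequal-share scenarios, in either direction. It does not move if non-implant shares and mortality are equal across arms. The documents do not support a claim that the loss favors one device: that depends on the non-implant shares, the mortality of these subjects and the denominator, none of which is given.

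**What to change.** Amend Protocol 7.3 and 12 so that every randomized subject without a TAVR valve, including those converted to surgery, has vital and stroke status

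1. confirmed on or after day 365, counted from the index procedure, or from randomization if no procedure occurred (unless the redacted text already sets the origin); and
2. collected by telephone or from records through two years, for the two-year descriptive endpoints.

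**Cost.** An amendment with FDA and IRB approval (Protocol 13.8 and 13.9), and remote contacts for perhaps 15 to 38 subjects if 2–5% of 750 are not implanted. Section 7.5 already allows remote assessment. Subjects who have already exited would not be covered, and the past tense of SAP 1.6 suggests that there may be some.

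**Optional clarification.** SAP 2.3.1 could add that the lock waits until the last randomized subject has passed day 365 and every open 90-day mRS is recorded, or documented as missing, unless the redacted text already says so. With the visit at 90 ± 14 days (Protocol 7.10.1), the wait is at most 90 + 14 = 104 days after day 365, and only if a late stroke is open.
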